9.7.2 Secondary Efficacy Endpoints

For the secondary efficacy endpoints analysis, the descriptive statistic methods will be used along with calculating the 95% CI and independence testing. To compare the dynamic changes of the parameters obtained for the study groups, independent samples T-test will be used.

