## 1. LIST OF ABBREVIATIONS

Abbreviation	Explanation
ADR	Adverse Drug Reaction
AE	Adverse Event
ALT	Alanine Aminotransferase
AP	Arterial Pressure
APTT	Activated Partial Thromboplastin Time
AST	Aspartate Aminotransferase
BLQ	Below the Limit of Quantification
BMI	Body Mass Index
CI	Confidence Interval
CLcr	Creatinine Clearance
CRF	Case Report Form
CRO	Contract Research Organization
CS	Clinically Significant
ECG	Electrocardiogram
ESR	Erythrocyte Sedimentation Rate
FEV 1	Forced Expiratory Volume for a second
GCP	Good Clinical Practice
GGT	Gamma-glutamyltransferase
HBV, HCV	Hepatitis B and C
IC	Informed Consent
ICH	International Conference on Harmonization
ICH GCP	Guidelines for Good Clinical Practice of the International Conference on Harmonization
IEC	Independent Ethics Committee
ITT	Intent-to-treat
LME	Linear Mixed Effect Model
Mean	Mean value
N	Number of observations
PP	Per Protocol
PTT	Prothrombin Time
p-value	p-value for H 0 of test performed
SADR	Serious Adverse Drug Reaction
SAE	Serious Adverse Event
SAP	Statistical Analysis Plan
SD	Standard Deviation
SE	Standard Error
TESS	Treatment Emergency Sign and Symptom
VAS	Visual Analogue Scale
WHO	World Health Organization

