## 2. INTRODUCTION

This document contains further details to the statistical analyses described in the protocol LDP0114 and is the primary source of all statistical analyses for the study.

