## 7. STATISTICAL METHODOLOGY AND STATISTICAL ANALYSES

### 7.1 STATISTICAL METHODS

Statistical analysis will be done using statistical software R ([www.r-project.org](http://www.r-project.org)).

For the statistical analysis is planned to use descriptive statistics, confidence intervals for difference in proportion (See section 8 [1]), mixed-effect model, two sample t-test, one-sample t-test, Wilcoxon test, Mann-Whitney test, Fisher exact test, Shapiro-Wilk test and permutation tests (See section 8 [2]).

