### 7.2.4 Secondary Efficacy Analyses

Secondary efficacy analysis will be performed on the ITT population.

#### 7.2.4.1 Nighttime cough resolution rate by Day 8

Nighttime cough symptoms will be classified as **Absent** (<2 at six-point cough scale) or **Present** ( $\geq 2$  at six-point cough scale). For such derivation treatment groups will be compared using the Fisher exact test.

#### 7.2.4.2 Daytime and nighttime cough symptoms resolution by Day 4

Daytime and Nighttime cough symptoms will be classified as **Absent** (<2 at six-point cough scale) or **Present** ( $\geq 2$  at six-point cough scale). Resolution Daytime (<2 at scale) and Nighttime (<2 at scale) symptoms at Day 4 will be described by treatment groups. Treatment groups will be compared using the Fisher exact test.

#### 7.2.4.3 Change in severity and frequency of daytime and nighttime cough on Day 4 and Day 8 from baseline on Day 1

Scores from the six-point cough scale will be described by visits and treatment groups together with changes from baseline (Day 1). Within group change will be tested using paired t-test (normal data) or Wilcoxon sign test (violation of normality), between groups test – two sample t-test (normal data) or Mann-Whitney test (violation of normality). Test for normality – Shapiro-Wilk.

Treatment groups will be also compared at baseline (Day 1). In case of significant difference (statistically) in scores/values at baseline a mixed-effect model will be

discussed.

Parameter dynamics also will be presented with graphics (see Figure 9.1).

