#### **7.2.4.4 Cough intensity change according to the visual-analogue scale on Day 4 and Day 8 from baseline on Day 1**

Analysis is similar to 7.2.4.3.

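### Secondary change endpoints are compared without the Day 1 value as covariate, an undefined model is only discussed after a significant Day 1 test, and the protocol's 95% CI is missing from the SAP text and shells

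*SAP*

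**What the plan says.** Protocol 9.7.2 plans descriptive statistics for the secondary efficacy endpoints "along with calculating the 95% CI and independence testing", without saying what quantity the interval is for. For changes over time it states that "independent samples T-test will be used".

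SAP 7.2.4.3 keeps the comparison of change from Day 1 but makes the test depend on Shapiro-Wilk: "two sample t-test (normal data) or Mann-Whitney test (violation of normality". It also tests the arms against each other at Day 1, and then: "In case of significant difference (statistically) in scores/values at baseline a mixed-effect model will be" discussed. No significance level is given for that Day 1 test. SAP 7.2.4.4 (VAS) and 7.2.4.5 (FEV1) each say only "Analysis is similar to 7.2.4.3".

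The model otherwise appears as an abbreviation in SAP 1 ("Linear Mixed Effect Model") and in the list of methods in SAP 7.1 ("mixed-effect model, two sample t-test, one-sample t-test, Wilcoxon test"). No section gives its fixed or random terms. The heading of SAP 4 mentions covariates, but none is listed.

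Shells 9.12 to 9.14 hold per-arm summaries, a within-arm p-value and a between-arm p-value. Shells 9.10 and 9.11 (resolution rates) hold counts and a Fisher p-value. Among the efficacy shells only 9.8 and 9.9, for the primary endpoint, have a row for the difference between arms with a CI.

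**The concern.** Three things are at issue.

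- **No covariate.** Subtracting the Day 1 value is not the same as adjusting for it. A patient with a high Day 1 score tends to fall further, so a chance Day 1 difference between arms carries over into the comparison of changes. Adjustment removes this and usually narrows the interval, using data already collected.
- **A trigger with nothing specified behind it.** A significant Day 1 test leads to a discussion of a model whose terms are unstated. In an open-label trial this leaves open whether the model is fitted, in what form, and whether it replaces the planned test. An imbalance that just misses significance gets no attention at all.
- **No estimate of the difference.** A non-significant between-arm p-value does not show that the arms are similar. In a non-inferiority trial the difference with its CI is what a reader can interpret, and the protocol mentions a CI.

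**Working it through.** **The plan's own figure.** Protocol 9.2 with z = 1.96 and 0.84, 70% in both arms and margin 20%: (1.96 + 0.84)² × (0.21 + 0.21) / 0.20² = 82.32 per arm; 82.32 / 0.9 = 91.5, so 92 per arm and 184 in total. This reproduces. It concerns the primary endpoint only and does not depend on the present point.

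**Inputs.** From the documents: 92 per arm, a daytime score of at least 3 at entry (protocol 4.2), and 70% at score 0 or 1 on Day 8. Not in the documents, so assumed: SDs, the Day 1 to follow-up correlation r, the nighttime distributions, and 0.05 for the Day 1 test.

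**How often the trigger fires by chance.** The shells carry five Day 1 between-arm tests: daytime, nighttime, VAS, FEV1 in litres and FEV1 in %. If fully correlated, 5%. If independent, 1 − 0.95⁵ = 0.226, or 23%. The truth lies between.

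**Precision.** Let k = SD at Day 1 / SD at follow-up. The variance ratio of ANCOVA to change score is (1 − r²)/(1 + k² − 2rk), and the CI width ratio is its square root. The two methods coincide when r = k.

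- *VAS and FEV1, equal SDs (k = 1).* The variance ratio becomes (1 + r)/2: 0.65, 0.75 and 0.95 at r = 0.3, 0.5 and 0.9. The CI is 19%, 13% and 2.5% narrower.
- *Daytime score.* Simulation, 8,000 trials per scenario, no treatment effect; Day 1 scores 3/4/5 with probabilities 0.55/0.35/0.10, and 70% at 0 or 1 on Day 8 (k = 0.57). Width ratios are 0.927, 0.972 and 1.000 at r = 0.16, 0.33 and 0.51, so 7%, 3% and 0% narrower. Half-widths go from 0.37 to 0.34, 0.33 to 0.32, and 0.30 to 0.30 points.
- *Nighttime score, same Day 8 rate assumed.* Width ratios are 0.735 to 0.838 if Day 1 scores span 0 to 5, 0.873 to 0.974 for 1 to 4, 0.905 to 0.992 for 2 to 4, and 0.968 to 1.001 for 2 to 3. Varying the Day 8 rate from 50% to 85% as well, the CI is 0 to 36% narrower.

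These figures compare ANCOVA with the interval that belongs to the protocol's t-test. For the integer scores, Shapiro-Wilk rejected normality in every simulated trial checked (300 per scenario), so under the SAP those endpoints would in practice receive a rank p-value.

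**Validity overall.** With normal data and no treatment effect, the change-score t-test had a type I error of 4.7% to 5.5% (20,000 trials per correlation). For the scores, Mann-Whitney had 4.4% to 5.6% and ANCOVA 4.4% to 5.5%.

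**Sensitivity to Day 1 imbalance.** The largest imbalance that stays non-significant is about 1.96 × √(2/92) = 0.29 SD. With equal SDs it shifts the difference in change by (1 − r) × 0.29 SD: 0.20, 0.14 and 0.09 SD at r = 0.3, 0.5 and 0.7.

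- In trials with Day 1 p between 0.05 and 0.20, the t-test's false-positive rate was about 10%, 9% and 8% at those correlations.
- In trials with a significant Day 1 test it was about 26%, 17% and 12%, against 4% to 6% for ANCOVA.
- For the scores, in near-miss trials (Day 1 |z| of 1.5 to 1.96, about 8 to 9% of trials per variable), Mann-Whitney had 5% to 8% for daytime at the 70% rate and 4% to 15% for nighttime over all scenarios, against 4% to 6% for ANCOVA. The Monte Carlo standard error is about 1 point.

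**The case against.** The strongest reply is that the unadjusted comparison is the protocol's own choice, that change scores already subtract the Day 1 value, that the tests hold their level, and that only unpowered secondary endpoints are involved. All of this stands. ANCOVA is a better method here, not the correction of an invalid one. On covariate adjustment the SAP follows the protocol; it departs from it by adding the Shapiro-Wilk switch and by leaving out the CI.

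On the CI, SAP 2 says that the SAP "is the primary source of all statistical analyses for the study". A reader might infer that the SAP thereby cancels the protocol's 95% CI. That goes too far: the same sentence presents the SAP as adding detail to the protocol's analyses, and nothing withdraws the interval. The footnote to SAP 9 lets tables differ from the templates, and an unadjusted interval could be worked out from the shelled N, means and SDs. What remains is that no SAP text or shell asks for a CI on these endpoints. Figure 9.1 is not shown, so its content cannot be checked.

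Two other strong readings also fail. A reader might infer an inflated type I error or a biased comparison; over all randomisations there is neither, and the excess appears only in trials with a chance Day 1 imbalance. A reader might also infer that the trigger depends on outcome data; it uses Day 1 data only. What is open is what happens after it fires.

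The size of the gain is also fairly questioned. It rests on assumed inputs, and for the daytime score, the variable best tied to the documents, it is small.

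**Conclusion.** The point holds as a worthwhile, low-cost improvement to the secondary analyses. Three facts need no assumption: the Day 1 value is not a covariate, the conditional model has no stated terms, and the protocol's 95% CI is absent from SAP 7.2.4 and shells 9.10 to 9.14.

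The size does rest on assumptions. Chance fires the trigger in 5% to 23% of trials, taking 0.05 as its level. The interval could be 0 to 7% narrower for the daytime score at the planned 70% rate. For nighttime score, VAS and FEV1 the gain runs from nil to large, depending on SDs and correlations that the documents do not give. The primary non-inferiority test and N=184 are unaffected.

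**What to change.** - Pre-specify a single analysis, applied whatever the Day 1 p-value: ANCOVA of the Day 4 value and of the Day 8 value (Day 8 only for FEV1) on treatment and the Day 1 value. Use ITT patients with the relevant observed values, since SAP 6.1 plans no replacement of missing data.
- Add the adjusted Levopront minus Libexin difference with its 95% CI to shells 9.12 to 9.14, and the difference in proportions with its 95% CI to shells 9.10 and 9.11.
- Delete the baseline-significance trigger and the Shapiro-Wilk switch. Keep the rank-based test of the 0 to 5 scores as a pre-specified sensitivity analysis.

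The cost is SAP wording and an added estimate with CI in five shells, with no extra patients, visits or measurements. The downside is a departure from the t-test in protocol 9.7.2, which must be documented as protocol 9.10 and SAP 7.4 require. Because data from the first part of the study have already been analysed, the protocol's unadjusted t-test should be kept as a supportive result, so that readers can see the change of method is not driving the conclusion.

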#### **7.2.4.4 Cough intensity change according to the visual-analogue scale on Day 4 and Day 8 from baseline on Day 1**

Analysis is similar to 7.2.4.3.

#### **7.2.4.5 Change of FEV1 on Day 8 from baseline values on Day 1**

Analysis is similar to 7.2.4.3.

### **7.3 SAFETY ANALYSIS**

Analysis will be performed for the safety population.

#### **7.3.1 Adverse Events**

Adverse Events will be summarized by treatment groups. Relation of AE to the therapy will be defined by AE onset date and period start date for the patient. All AEs will be coded with MEDDRA dictionary. AEs will be summarized by SOC (System Organ Class) and PT (Preferred Terms).

Adverse Events (if any) started before the first dose of the study drug(s) will be presented in the separate table.

AE frequencies will be compared between treatment groups. For such comparisons MedDRA Preferred Terms (PT) will be used. Treatment groups will be compared by set of frequencies of PT terms using permutation tests. One p-value will be provided ( $H_0$ : treatment groups are equal in set of AE frequencies).

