3.1.1 Study Design

The study will consist of 3 periods: screening and randomization, study therapy, follow-up.

3.1.1.1 Screening and Randomization.

At Visit 1, Day 1 after signing the Informed Consent Form, the patients will be screened for assessment of inclusion/exclusion criteria. Demography, medical history, and information on concomitant medications will be collected; physical examination, vital signs, weight and height measurements will be performed; blood and urine samples for laboratory tests will be collected; the cough severity and frequency rate will be assessed using the "Six-point daytime and nighttime cough assessment scale"; cough intensity will be assessed using the visual-analogue scale; ECG and spirometry will be performed (pre- and post-bronchodilator) along with the chest x-ray or fluorography. Women of childbearing potential will take the pregnancy test before conducting the chest x-ray or fluorography.

According to the study schedule (considering acute condition of patients), screening and randomization will be performed in one day. Patients meeting all inclusion/exclusion criteria will be randomized into two groups (at a 1:1 ratio)

- Levopront® syrup 30 mg/5 ml — 10 ml t.i.d. for 7 days
- Libexin® 100 mg tablets — 1 tablet t.i.d. for 7 days

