3.1.1.2 Study Treatment Period

The study drugs will be taken 3 times a day (with the interval of not less than 6 hours, between meals) during 7 days. The first study drug administration will be performed at the clinical site on the day of randomization; the last study drug administration will be performed in the evening before Day 8.

During the study treatment period, patients will keep a diary on a daily basis and fill in the cough severity and frequency data, body temperature, study drug dosing, concomitant medications and adverse events. Cough severity and frequency assessment should be performed in the morning after waking up using the "Six-point daytime and nighttime cough assessment scale" provided in the Diary and in the evening before retiring to bed. Patients will visit the clinical site on Days 4 and 8 for assessment of efficacy and safety parameters. Patients should bring the completed Diary and the unused study drug at each visit. During the visits, physical examination will be performed, vital signs will be assessed, cough severity and frequency assessment will be performed using the "Six-point daytime and nighttime cough assessment scale", and also cough intensity assessment will be made using the visual-analogue scale. On Day 8, blood and urine samples for laboratory tests will be collected, spirometry (without-bronchodilator) will be conducted, and then the study treatment period will be completed. If necessary, patients will continue treatment according to the local standards of medical care.

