6.12.3 Reporting AEs and SAEs

At every visit, patients should report any AEs, responding to open, non-probing questions (e.g. How have you been doing since the last visit?). For each AE/SAE reported by a patient, the Investigator should collect and document in source documents and CRF all the needed information, including diagnosis and symptoms, date of onset and date of resolution, outcome, severity, criteria of seriousness, circumstances, that may denote possible relatedness to the study drug and concomitant therapy, underlying diseases or concomitant conditions, study procedures or other causes, actions related to the study drug, pharmaceutical treatment, medical interventions, results of laboratory and instrumental tests for AE, other circumstances, which may add to comprehensive description of the event

Within the period of self-administration of the study drug, patients will enter information about possible adverse events in a diary.

Increase in severity of the ongoing adverse event shall be considered a new AE. The date of further worsening in severity will be the start date of the new AE, and the previous day shall be the end date of the original AE.

The date of onset of SAE is the date of onset of the seriousness criterion. The preceding condition, if applicable, should be reported as a non-serious AE.

If an AE is serious, Investigator should also promptly submit a SAE report (specifying the seriousness criteria), within 24 hours from first knowledge to the IPHARMA Medical Monitor. New information about SAE which becomes known later, should be reported to the Sponsor in the same way and in the same time. Besides, the Sponsor should be provided with certified

copies of source documents for that SAE (hospital discharge summary, autopsy report, death certificate etc.). Data in source document and SAE form shall be duly anonymized.

AEs should be followed up and reported from the date of signing informed consent to the last visit or study related procedure (teleconference at follow-up). Any AE or SAE which is spontaneously reported by a patient within 30 days after the last study visit, will be reported and assessed in the same way as AEs occurring during the study. AEs should be reported until resolution or stabilization of patient's condition.

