6.12.5 AE Relatedness to the Study Drug

For each AE the Investigator should assess its possible causal relationship to the study drug according to the Modified WHO scale/ICH E2B, shown in Table 4.

Table 4. Causal Relationship to the Study Drug

AE Category	Definition
1. None (Intercurrent Event)	An event that is not and cannot be related to the Investigational Product, e.g. patient is a passenger in a road traffic accident.
2. Unlikely (remote)	Relationship is not likely e.g. a clinical event including laboratory test abnormality with temporal relationship to drug administration which makes a causal relationship improbable and in which other drugs, chemicals or underlying disease provide more plausible explanations
3. Possible	Relationship may exist, but could have been produced by the patient's condition or treatment or other cause
4. Probable	Relationship is likely, the AE abates upon discontinuation of Investigational Product and cannot be due to the patient's condition
5. Highly Probable	Strong relationship, the event abates upon discontinuation of Investigational Product and, if applicable, re-appears upon repeat exposure

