**Table 9.32 Adverse Events (including SAE) started before the first dose of the study drug(s). Safety population. N = xx**

MEDDRA System Organ Class term MEDDRA Preferred term	Levopront ® (T) n (%)		Libexin ® (C) n (%)	
	x (%)	Y	x (%)	Y
SOC term	xx (xx.x)	xx	xx (xx.x)	xx
Preferred term 1	xx (xx.x)	xx	xx (xx.x)	xx
Preferred term 2	xx (xx.x)	xx	xx (xx.x)	xx
...				

X = Number of subjects having at least one AE from the group.  
 % = Percent of patients having at least one AE from the group  
 Y = Total number of events

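### SAP 7.3.1 sorts adverse events by date against an undefined period start, but consent, screening and first dose share Day 1, so dates cannot separate Day 1 events that began before the first dose from those that began after it

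*SAP*

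**What the plan says.** SAP 7.3.1 gives one timing rule for adverse events: "Relation of AE to the therapy will be defined by AE onset date and period start date for the patient". It does not say which period is meant, when that period starts, or on which side an onset on the start date falls. The section then requires a separate display: "Adverse Events (if any) started before the first dose of the study drug(s) will be presented in the separate table". The shell is Table 9.32.

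The protocol puts everything relevant on one day:

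- Section 3.1.1 on consent and screening: "At Visit 1, Day 1 after signing the Informed Consent Form, the patients will be screened for assessment of inclusion/exclusion criteria". It adds that "screening and randomization will be performed in one day".
- Section 3.1.1.2 on dosing: "The first study drug administration will be performed at the clinical site on the day of randomization".
- Section 6.12.1 starts adverse event collection at consent and notes that this precedes the first dose.
- Section 6.12.3 asks the investigator to record the needed information on each event, "including diagnosis and symptoms, date of onset and date of resolution, outcome, severity" among other items. No clock time is named.

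SAP 6.2.1 judges incomplete onset dates against the informed consent date. It counts an event with a missing onset date as treatment-emergent.

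On causality, Protocol 6.12.5 states: "For each AE the Investigator should assess its possible causal relationship to the study drug". The scale in Protocol Table 4 has five categories.

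**The concern.** A date comparison can sort events around the first dose only if some pre-dose events carry an earlier date. Here a pre-dose event normally carries the same date as the dose.

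The Day 1 events are the ones for which the distinction matters most. Before the first dose the patient has blood drawn and performs spirometry before and after a bronchodilator. After it comes the window for immediate reactions. Protocol 3.3.4 lists anaphylactoid reactions and angioedema among the risks of Levopront, and bronchospasm and angioedema among those of Libexin. A wrong rule either charges effects of screening procedures to the study drugs or files a first-dose reaction as something that preceded the drug.

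The wording is a second, smaller problem. The sentence speaks of relation to therapy, the term normally used for causality, while describing a comparison of dates. The SAP calls itself the primary source for all statistical analyses, so a programmer could follow the sentence literally.

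**Working it through.** No stated figure needs reproducing. The check is logical.

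**Inputs.** Consent date = randomisation date = first-dose date = Day 1 (Protocol 3.1.1 and 3.1.1.2). Collection starts at consent (6.12.1), so the earliest possible onset date is Day 1. Scheduled follow-up ends with the Day 10 telephone contact. Later spontaneous reports do not affect the argument.

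**Which period start.** The study has three periods: screening and randomisation, therapy, and follow-up. The first two both begin on Day 1, so choosing either gives the same date. The missing definition cannot be repaired by interpretation.

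**Two possible comparisons.** Section 7.3.1 gives no comparison sign. As printed, the table in 6.2.1 uses a strict later-than for one condition and a same-or-later for others, so the sign cannot be inferred from there. Apply both to onset dates Day 1 to Day 10:

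| True situation | Pre-dose if onset date < first-dose date | Pre-dose if onset date ≤ first-dose date |
|---|---|---|
| Day 1, before the dose | classed as post-dose (wrong) | classed as pre-dose (right) |
| Day 1, after the dose | classed as post-dose (right) | classed as pre-dose (wrong) |
| Day 2 to Day 10 | classed as post-dose (right) | classed as post-dose (right) |
| Onset dates that enter Table 9.32 | none | all of Day 1 |

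Under the first rule Table 9.32 is empty for every patient on the one-day schedule. Under the second it takes in reactions to the first dose. Neither rule gets both Day 1 rows right.

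**Anchors.** Section 6.2.1 uses the consent date, Table 9.32 the first dose, and 7.3.1 an undefined period start. On the one-day schedule the first two share a date, so the consent anchor alone moves no event. It would matter for a patient whose recorded consent is on an earlier day. That could arise through the single re-screening allowed in Protocol 7.1.1, although the documents do not say which consent date would then apply.

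**Causality.** Table 9.33 counts as related the events rated possible, probable or highly probable, which are categories of Protocol Table 4. Tables 9.36 and 9.39 report relation to study drug separately. Protocol 9.8 also tabulates by relationship. The rating therefore survives in the planned output.

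**Size.** The documents give no rate of pre-dose or Day 1 events. As an assumption only, if 1% to 5% of the 184 patients had a pre-dose event, that would be 0.01 × 184 = 1.8 to 0.05 × 184 = 9.2, or about 2 to 9 patients over both arms.

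**The case against.** The strongest reply is that the data may already allow the separation. The list in Protocol 6.12.3 is open-ended and also asks for circumstances bearing on relatedness. The CRF is not among the documents. Protocol 7.1.1 lists adverse event assessment twice at Visit 1: once before enrolment, and again after dispensing and first dose. Protocol 6.3 and 6.12.11 send conditions and abnormalities found at screening to medical history, which shrinks the set of pre-dose events. All of this stands. It rules out saying that Day 1 events cannot be separated at all, or that only a date is collected. What remains is that the stated date rule cannot separate them and that the SAP refers to none of these other sources.

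A second reply is that the sentence requiring Table 9.32 states no date rule of its own. That is correct, but the only timing rule the SAP supplies is the one in the preceding text, and it offers no other.

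A third is that little is lost. Tables 9.33 to 9.39 carry no stated restriction to treatment-emergent events, so it is an inference that a Day 1 event classed as pre-dose would drop out of them. It would in any case appear by arm in Table 9.32 and in the listings. The default for missing onset dates also points away from the on-or-before reading. This limits the harm to misfiling, and it stands.

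A reader might also infer that the SAP replaces the investigator's causality rating with a date rule. Read alone, the sentence invites that, but Tables 9.33, 9.36 and 9.39 show otherwise.

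**Conclusion.** The point holds for the timing rule. For patients who follow the one-day schedule, comparing dates cannot tell Day 1 events before the first dose from those after it, and Table 9.32 cannot be filled correctly that way. The undefined period start and the consent-date anchor in 6.2.1 belong to the same defect. The causality issue is one of wording only.

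The size is unknown and probably a few events; the range of 2 to 9 patients rests wholly on an assumed 1% to 5%. A reader might be tempted to scale it from the suspected reactions reported in Protocol 3.3.2, 60 of 2868 patients. That figure covers 1 to 22 days of levodropropizine exposure and measures neither Day 1 nor pre-dose events, so it should not be used here.

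The consequence is confined to a few entries in the safety tables and, if those tables exclude events classed as pre-dose, to the between-group permutation test on adverse event frequencies. The primary non-inferiority result is not affected. The change should be made before database lock. The conclusion assumes that the CRF provides nothing that the SAP already intends to use but does not mention.

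**What to change.** Amend the SAP as follows:

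- **Definition (7.3.1).** An adverse event is treatment-emergent if its onset is at or after the first dose of study drug. Events with onset before the first dose go to Table 9.32. State whether Tables 9.33 to 9.39 are restricted to treatment-emergent events.
- **Day 1 onsets.** Classify them by a before/after-first-dose flag or by onset time. Add this to the adverse event page if the CRF does not already capture it.
- **First part of the study.** Visits there finished on 27 April 2017, so take the timing from source notes or from the two Visit 1 assessments. An event recorded at the pre-enrolment assessment is pre-dose. One first recorded at the later assessment still needs its onset checked.
- **Unknown timing.** Count as after the first dose, in line with the SAP's own default for missing onset dates.
- **Section 6.2.1.** Replace the consent-date anchor with the first dose and use one comparison sign throughout.
- **Wording.** Replace the sentence on relation to therapy with a statement that the relation tables use the investigator's category from Protocol Table 4.

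The cost is a few SAP sentences, possibly one CRF field for the second part, and a small source check of Day 1 events from the first part.
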